#### ***4.3 Inclusion Criteria***

1. Male or female.
2. Age 21-65 years old.
3. Established diagnosis of functional dyspepsia, idiopathic or diabetic gastroparesis as per AGA (American Gastroenterology Association) guidelines.
4. Patient is capable of giving informed consent and undergo upper endoscopy.
5. Patient is on stable doses of other medications for gastroparesis for preceding 4 weeks prior to enrollment (baseline measures).

#### **4.4 Exclusion Criteria**

1. Surgical-related gastroparesis
2. Extrinsic myopathy or neuropathy causing gastroparesis.
3. Use of narcotic pain medications in the preceding 2 weeks of study enrollment.
4. Patients with enteric feeding tubes or requiring parenteral nutrition.
5. Patients with severe flare requiring hospitalization.
6. Untreated significant depression or suicidal thoughts.
7. Pregnant or breast-feeding women.
8. History of gastric pacemaker implantation.
9. Patients with prior gastric surgery, including fundoplication, partial/total gastrectomy, or gastric bypass.
10. Patients with malabsorption of enteric, pancreatic, or hepatobiliary etiology.
11. Patients with primary pulmonary disorders that affect the spirulina breath test.
12. Patients with implantable electronic devices.
13. Patients with carotid artery atherosclerosis.
14. Patient with HX of embolic stroke or TIA, arterial vascular disease, active unexplained neurologic symptoms, or men 65 above who smoke tobacco.
15. Any patient who has had a botox injection in their abdominal region within the past 6 months prior to enrollment.

#### **4.5 Subject Recruitment and Screening**

Patients seen at the Stanford University Digestive Health Clinic in the Principal Investigator's clinical practice will be screened for appropriateness in the study and recruited. Those meeting eligibility criteria will be recruited. Informed consent will be obtained and the patients will be scheduled for first upper endoscopy and instructed on the use of the GCSI questionnaire and other surveys. After baseline endoscopy is completed, patients will return to clinic for blood sample collection, including complete blood count, comprehensive metabolic panel, serum or urine  $\beta$ -HCG (women of reproductive age only), ESR, CRP, serum cytokines (Human 63-plex Luminex assay custom-built by eBioscience), and two additional blood vials for flow cytometry and in-vitro re-stimulation assays, and a third vial for blood banking. Banked blood in the [name] lab will be used for subsequent studies of exploratory markers of inflammation, immunity, metabolism, and neurotransmission. No genetic testing will be done with fresh or banked patient samples. Stool collection and saliva collection will also occur. At this same visit, patients will undergo HRV testing and gastric emptying testing, which are non-invasive and office-based tests. Patients will then be given the gammaCore vagal nerve stimulator and be instructed on its use with a first time stimulation in the office and a repeat blood collection 90-120 minutes later. Patients will then self-administer daily VNS twice a day for total of 4 weeks' duration.

#### **4.6 Early Withdrawal of Subjects**

1. Patients may withdraw from the trial at any time.
2. Patients must be withdrawn from the trial for any of the following:
  - The patient withdraws consent.

- The patient develops serious adverse effect (none anticipated) during the study period.

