#### ***3.4 Study Duration***

1. Up to 8 weeks for screening period and baseline measures
2. Four weeks of active VNS therapy
3. Four weeks follow up period following discontinuation of therapy

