### 5.2 Treatment Regimen

1. Patients seen at Stanford University Digestive Health Center who meet study inclusion criteria will be screened for enrollment. Those patients with diagnosed functional dyspepsia, idiopathic or diabetic gastroparesis will be considered eligible. Those who do not meet any exclusionary criteria will then be actively enrolled in the study. Study subjects who sign informed consent to participate in the study will have a baseline history and physical exam, and baseline laboratory tests to be completed after baseline endoscopy and at the time of first (pre-treatment) gastric emptying testing.
2. Patients will complete the following forms at the time of study enrollment:
  - GCSI-DD (Gastroparesis Cardinal Symptom Index Daily Diary)
  - GI PROMIS belly pain questionnaire.
  - PROMIS Global Health Short Form questionnaire.
  - PROMIS Pain Interference Short Form 8a questionnaire.
  - Short Form SF-12 questionnaire.
  - Compass 31 Survey
3. After successful baseline upper endoscopy and subsequent gastric emptying testing with associated baseline HRV, blood, urine, saliva, and stool tests, patients will start active VNS treatment. The first gammaCore device therapy will be done in the office to ensure proper use, tolerability, and address any questions or concerns patients may bring up. The dosing of therapy will be personalized for each patient at this first session (by asking subject to increase dose until they experience a tug on the ipsilateral side of their mouth). This dose will then be maintained for the duration of the study. Posteriorly, 90-120 minutes after the first stimulation, a repeat blood collection will take place (two vials for Human 63-plex Luminex assay and banking) to assess the acute effect of the VNS treatment on inflammatory markers.

4. Total treatment duration will be 4 weeks. GammaCore administration will occur twice daily, in the morning and evening. Each treatment will entail a 2-minute application to the R and L cervical vagus nerve, each side separated by 3-5 minutes, for a total of 4 applications daily (total of 8 minutes).
5. Patients will receive weekly calls to assess compliance, tolerability, and reminders for their symptoms questionnaires.

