6. Patients will present to endoscopy for their post-treatment upper endoscopy 4 weeks after initiation of therapy. No later than 3 days after endoscopy, patients will present to clinic at which time post-treatment gastric emptying testing, HRV testing, and laboratory tests (blood and stool) will be obtained, and the aforementioned forms will again be completed.
7. Patients will be seen in clinic again at 4 weeks after discontinuation of therapy, and undergo a repeat medical history and physical exam. At this time gastric emptying testing, HRV testing, and laboratory tests (blood and stool) will again be obtained; and the aforementioned forms will again be completed to assess whether any change in symptoms and disease severity has occurred off therapy.

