	(baseline) Visit 1 Enrollment	≤ 8 wk prior (baseline) Visit 2 Endoscopy	Day 0 (start VNS) Visit 3 Clinic	Day 28 ( Visit 4 Endoscopy VNS 4 Weeks	Day 31 End VNS) Visit 5 Clinic	Day 51 (Washout) Visit 6 Clinic
Inclusion criteria met, no exclusion criteria met	X					
Informed consent	X					
Medical History	X		X		X	X
Physical Exam	X		X		X	X
Medication Rev	X		X		X	X
Blood collection: CBC, BMP, LFT, A1C, β-HCG, ESR, CRP, 63-plex Luminex ,and Heparin vials for FACS analysis			X	X		X
			X	X		X
			X	X		X
			X	X		X
			X	X		X
			X	X		X
Forms GI PROMIS pain PROMIS Health PROMIS Pain SF_12_Health COMPASS 31	X		X		X	X
	X		X		X	X
	X		X		X	X
	X		X		X	X
	X		X		X	X
	X		X		X	X
	X		X		X	X
GCSI-DD HRV-app	← 8 weeks. (2 weeks before VNS, 4 weeks of VNS, 2 weeks after VNS) →					
EGD		X		X		
HRV / EKG			X		X	X
Gastric Emptying			X		X	X
Stool collection			X		X	X
Saliva collection			X		X	

Adverse reactions	X	X	X	X	X	X

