### **6        Safety and Adverse Events**

#### **6.1    *Risks***

There is a low reported incidence of adverse side effects with the use of transdermal VNS using gammaCore. There have been no reported incidences of cardiac arrest, respiratory depression, or other serious adverse events. In an IDE, prospective, multi-centered pilot study, no adverse events were reported during or after stimulation. There were no significant changes in electrocardiogram, heart rate or systolic or diastolic blood pressure (Engel et al Poster). Reported side effects are mild and include hoarseness, shortness of breath, change in voice, & skin irritation.

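### Section 4.6 makes a serious adverse effect a mandatory exit from the trial, not just from the device, and nothing provides for following the event to its outcome

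*Combined protocol and SAP*

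**What the plan says.** Section 4.6 opens its list of compulsory exits with "Patients must be withdrawn from the trial for any of the following". The list has two entries. One is withdrawal of consent. The other is "The patient develops serious adverse effect (none anticipated) during the study period". No device-only discontinuation is described there or anywhere else.

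The study period runs beyond treatment. Section 3.4 includes "Four weeks follow up period following discontinuation of therapy", and Section 5.2 item 7 adds "Patients will be seen in clinic again at 4 weeks after discontinuation of therapy, and undergo a repeat medical history and physical exam".

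Safety observation of enrolled patients has three parts:

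- Section 5.2 item 5: "Patients will receive weekly calls to assess compliance, tolerability, and reminders for their symptoms questionnaires".
- The schedule table under Study Assessment and Monitoring: a row headed "Adverse reactions", marked at all six visits, with physical examinations and blood collections at some of them.
- Section 6.2: the investigator watches for new events, grades them, acts on them, judges whether the study caused them, and reports them.

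Sections 6.2 and 6.3 also require yearly reports. These cover the events, the reasons for withdrawal, the number of dropouts and a short status for each enrolled patient.

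**The concern.** Stopping a treatment and leaving a study are different decisions. After a serious adverse effect, stopping the device is the natural protective step. Ending study observation as well gives the patient no further protection, and it removes the scheduled contacts that would show how the event turned out.

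Safety and tolerability are objective 9 in Section 3.2 and endpoint 2.3 in Section 3.3. For an investigational device tested in 45 patients, a single serious event would carry much of the safety evidence. A reader would want to know whether it settled, and whether it settled once stimulation stopped. The second question also bears on the attribution that Section 6.2 asks the investigator to make. The plan secures the record that the event happened. It does not secure the answer to either question.

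**Working it through.** The plan gives no figure to reproduce. The check has two parts: a comparison of the text, and a count from the visit schedule.

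**1. Does any other provision supply follow-up of a serious event?**

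| Provision | What it covers | Follow-up to outcome after withdrawal? |
|---|---|---|
| 4.6 | Compulsory exit from the trial | No; it ends participation |
| 5.2 item 5 | Weekly tolerability calls | Not extended to withdrawn patients |
| 5.2 item 7 | Clinic visit 4 weeks after therapy ends | Not extended to withdrawn patients |
| Schedule table | Adverse-reaction check at each of six visits | Nothing off schedule or after withdrawal |
| 6.2 | Detection, grading, immediate action, attribution, report within 15 calendar days | Onset and first handling only |
| 6.2 and 6.3, yearly reports | Events, withdrawal reasons, dropout numbers, brief patient status | Reporting items; they set no visit and no duration |

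None of these requires an event to be followed until it resolves or stabilises.

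**2. How much scheduled safety observation is exposed?**

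The inputs are the visits marked in the schedule table. Treatment starts at Visit 3. If an event occurs during treatment and before Visit 4, the visits still to come are 4, 5 and 6. If it occurs after Visit 5, only Visit 6 remains. For each item, the maximum loss is the number of marked visits still to come, out of all marked visits.

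| Item | Visits marked | Event during treatment | Event after Visit 5 |
|---|---|---|---|
| Adverse-reaction check | 1, 2, 3, 4, 5, 6 | 4, 5, 6: up to 3 of 6 | 6: 1 of 6 |
| Physical examination | 1, 3, 5, 6 | 5, 6: up to 2 of 4 | 6: 1 of 4 |
| Blood collection | 3, 4, 6 | 4, 6: up to 2 of 3 | 6: 1 of 3 |

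Four notes on the count:

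- Section 5.2 item 6 puts the post-treatment laboratory tests at the clinic visit (Visit 5) rather than at Visit 4. The marked visits are then 3, 5 and 6, and the counts are the same.
- The repeat blood draw 90 to 120 minutes after the first stimulation is not counted.
- The table heads the last visit "Day 51 (Washout) Visit 6 Clinic", while Section 5.2 item 7 places it four weeks after therapy stops. The count is in visits, so it does not depend on which date is right.
- Gastric emptying and heart rate variability tests are left out. The plan assigns them to endpoints 1.2 and 2.4, which concern the effect of stimulation. The blood row is kept because it includes blood count, metabolic and liver tests, although part of it serves inflammation endpoint 2.5.

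The documents give no serious-event rate, so the number of affected patients is not estimated.

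**The case against.** The strongest reply is that only the compulsory exit is written down, and that loss of the outcome is inferred from silence. A reader might conclude that the outcome of every serious event will be lost. The documents do not support that. They nowhere forbid clinical contact after withdrawal, and Section 4.5 recruits from the investigator's own clinic, so informal follow-up is plausible. The yearly report to the FDA also asks for the status of each enrolled patient, not only of those still in the trial. The consent form was not available for this review and may contain follow-up terms. This objection stands to the extent that the counts are an upper bound.

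A second reply concerns wording. Section 4.6 speaks of an adverse effect, whereas Section 6.2 speaks of adverse events. Section 4.6 may therefore be meant only for effects of stimulation, which would narrow its reach in the off-therapy weeks. The text is ambiguous. The literal reading covers the whole study period, but the point does not depend on it, because the gap during treatment is there on either reading.

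A third reply is that endpoint 2.3 is defined by the recording of events, and a withdrawn patient's event is recorded. That is correct: the endpoint as written is met. What is missing is the outcome of the event.

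Finally, removing a patient after a serious effect is cautious, particularly with a repeat endoscopy and biopsies still to come. That is a good reason to stop the device and reconsider the endoscopy. It is not a reason to stop the safety checks.

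**Conclusion.** The point holds and is minor. Section 4.6 compels exit from the trial where stopping the device would do, and no provision secures follow-up of the event to resolution or stabilisation. Per affected patient, the exposure is at most 3 of 6 adverse-reaction checks, 2 of 4 physical examinations and 2 of 3 scheduled blood collections for an event during treatment. For an event after Visit 5 it is one of each.

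These maxima assume that Section 4.6 is applied literally and that no contact takes place after withdrawal. The practical effect is probably small. Section 4.6 anticipates no serious effects, and Section 6.1 says of the device: "There have been no reported incidences of cardiac arrest, respiratory depression, or other serious adverse events". Patients with non-serious effects are not subject to the rule.

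A reader might also infer that the rule biases the symptom or gastric emptying results. A withdrawn patient's later values could indeed be missing, but with no serious-event rate in the documents and none expected, there is no basis for claiming a bias, and none is claimed.

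**What to change.** Rewrite the second entry in Section 4.6 so that a serious adverse effect is a reason to discontinue the device, not the study. Add that the event is followed to resolution or stabilisation and its outcome recorded. Unless the patient withdraws consent, keep the patient on the remaining scheduled safety contacts to Visit 6: adverse-reaction checks, physical examinations, safety blood tests and tolerability calls. Omit the repeat endoscopy unless it is clinically appropriate.

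The cost is a short text change and, for any affected patient, a few follow-up contacts at visits already scheduled. The sample size and the primary analysis do not change.

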## 5 Study Device

### 5.1 Description

GammaCore is a hand held device used for transcutaneous vagal nerve stimulation. The manufacturer, electroCore, has regulatory approval for the use of gammaCore therapy in the acute and/or prophylactic treatment of cluster headache, migraine and medication overuse headache throughout the European Union, South Africa, India, New Zealand, Australia, Colombia, Brazil and Malaysia. In Canada the therapy is indicated for the acute and/or prophylactic treatment of cluster headache and for the treatment of migraine. It is not FDA-approved in the USA, but is registered as an investigational new device in various clinical trials. GammaCore is CE marked and indicated for the acute and/or prophylactic treatment of Migraine, Cluster, Hemicrania Continua and Medication Overuse Headache in adults. Thus, the purpose of this protocol is to provide VNS to patients with gastroparesis and functional dyspepsia. Our IDE number is: [REDACTED]. Our NCT number is: NCT03120325

### 5.2 Treatment Regimen

1. Patients seen at Stanford University Digestive Health Center who meet study inclusion criteria will be screened for enrollment. Those patients with diagnosed functional dyspepsia, idiopathic or diabetic gastroparesis will be considered eligible. Those who do not meet any exclusionary criteria will then be actively enrolled in the study. Study subjects who sign informed consent to participate in the study will have a baseline history and physical exam, and baseline laboratory tests to be completed after baseline endoscopy and at the time of first (pre-treatment) gastric emptying testing.
2. Patients will complete the following forms at the time of study enrollment:
  - GCSI-DD (Gastroparesis Cardinal Symptom Index Daily Diary)
  - GI PROMIS belly pain questionnaire.
  - PROMIS Global Health Short Form questionnaire.
  - PROMIS Pain Interference Short Form 8a questionnaire.
  - Short Form SF-12 questionnaire.
  - Compass 31 Survey
3. After successful baseline upper endoscopy and subsequent gastric emptying testing with associated baseline HRV, blood, urine, saliva, and stool tests, patients will start active VNS treatment. The first gammaCore device therapy will be done in the office to ensure proper use, tolerability, and address any questions or concerns patients may bring up. The dosing of therapy will be personalized for each patient at this first session (by asking subject to increase dose until they experience a tug on the ipsilateral side of their mouth). This dose will then be maintained for the duration of the study. Posteriorly, 90-120 minutes after the first stimulation, a repeat blood collection will take place (two vials for Human 63-plex Luminex assay and banking) to assess the acute effect of the VNS treatment on inflammatory markers.

4. Total treatment duration will be 4 weeks. GammaCore administration will occur twice daily, in the morning and evening. Each treatment will entail a 2-minute application to the R and L cervical vagus nerve, each side separated by 3-5 minutes, for a total of 4 applications daily (total of 8 minutes).
5. Patients will receive weekly calls to assess compliance, tolerability, and reminders for their symptoms questionnaires.
6. Patients will present to endoscopy for their post-treatment upper endoscopy 4 weeks after initiation of therapy. No later than 3 days after endoscopy, patients will present to clinic at which time post-treatment gastric emptying testing, HRV testing, and laboratory tests (blood and stool) will be obtained, and the aforementioned forms will again be completed.
7. Patients will be seen in clinic again at 4 weeks after discontinuation of therapy, and undergo a repeat medical history and physical exam. At this time gastric emptying testing, HRV testing, and laboratory tests (blood and stool) will again be obtained; and the aforementioned forms will again be completed to assess whether any change in symptoms and disease severity has occurred off therapy.

## **Study Assessment and Monitoring**

- 1. Spirulina Gastric Emptying Breath Test** (Viramontes et al 2001): Gastric emptying times will be measured at baseline and after 4-week therapy. As part of standard of care procedures, diabetic patients will have their blood sugar measured prior to this test. They will need to have a blood sugar level of less than 275 mg/dl, as this high level will results in artificially delayed emptying. Patients will be asked to reschedule if this is the case.
- 2. GCSI-DD[3]:** Gastroparesis-specific symptom severity scale. Obtained at baseline (1 week prior to randomization) and daily throughout the duration of the study.
- 3. GI PROMIS[2]:** publically available patient related outcome (PRO) measure that covers 8 symptom domains (Abdominal pain, Gas/Bloating, Diarrhea, Constipation, Bowel Incontinence, Reflux, Nausea and Vomiting, Disruptive Swallowing) that can be used together or individually to assess GI symptoms in clinical practice and research. Symptoms are assessed via 7-day recall. The questionnaire will be filled out one week prior to starting therapy and at each follow up visit.
- 4. PROMIS Global Health**
- 5. PROMIS Pain Interference**
- 6. Compass 31 Survey**
- 7. Human 63-plex Luminex assay:** The Human Immune Monitoring Center (HIMC) at the Stanford Institute for Immunity, Transplantation and Infection has a standardized immunoassay for the detection of 63 human serum cytokines and chemokines using a Luminex assay.
- 8. Flow Cytometry:** additional blood samples will be processed for storage, or for same-day in vitro re-stimulation assays in [name] research Laboratory at Stanford SOM.

**9. Dysbiosis:** stool samples will be frozen for storage until all subjects are enrolled. Subsequent metabolomics and 16S rRNA sequencing experiments will be done with collaborators of [name] at Stanford SOM.

**10. Upper GI Endoscopy:** All patients will receive standard of care and standard precautions for GI endoscopy as per Stanford Outpatient Endoscopy guidelines. Patients will undergo a baseline endoscopy, and again after VNS treatment to assess the impact of therapy on the target organ, i.e. the stomach. During the procedure, detailed endoscopic assessment of the mucosa will take place, including tissue biopsies that will be collected and processed in [name] at Stanford SOM.

	(baseline) Visit 1 Enrollment	≤ 8 wk prior (baseline) Visit 2 Endoscopy	Day 0 (start VNS) Visit 3 Clinic	Day 28 ( Visit 4 Endoscopy VNS 4 Weeks	Day 31 End VNS) Visit 5 Clinic	Day 51 (Washout) Visit 6 Clinic
Inclusion criteria met, no exclusion criteria met	X					
Informed consent	X					
Medical History	X		X		X	X
Physical Exam	X		X		X	X
Medication Rev	X		X		X	X
Blood collection: CBC, BMP, LFT, A1C, β-HCG, ESR, CRP, 63-plex Luminex ,and Heparin vials for FACS analysis			X	X		X
			X	X		X
			X	X		X
			X	X		X
			X	X		X
			X	X		X
Forms GI PROMIS pain PROMIS Health PROMIS Pain SF_12_Health COMPASS 31	X		X		X	X
	X		X		X	X
	X		X		X	X
	X		X		X	X
	X		X		X	X
	X		X		X	X
	X		X		X	X
GCSI-DD HRV-app	← 8 weeks. (2 weeks before VNS, 4 weeks of VNS, 2 weeks after VNS) →					
EGD		X		X		
HRV / EKG			X		X	X
Gastric Emptying			X		X	X
Stool collection			X		X	X
Saliva collection			X		X	

Adverse reactions	X	X	X	X	X	X

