### **3.2 Study Objectives**

1. Establish the effect of VNS on gastric emptying time and on cardinal symptoms of gastroparesis (nausea, vomiting, bloating, abdominal pain, and early satiety).
2. Assess the effects of VNS on various measures of quality of life, including global health and overall pain interference.
3. Investigate molecular and neuroimmune signaling pathways in different gastroparesis patients.
4. Determine the effects of VNS on measurable serum inflammatory markers and cytokines.
5. Determine the effects of VNS on measurable cytokines, nerve growth factors, and neurotransmitters in the gastric and duodenal submucosa.
6. To characterize the submucosal enteric nervous system in gastroparesis subtypes and identify novel neuro-immune interactions.
7. Determine if gastric emptying and symptom response to VNS is associated with changes in inflammatory markers and neuro-immune signaling.
8. Determine if there is a difference in response to VNS in patients with idiopathic vs. diabetic gastroparesis.
9. Evaluate the safety and tolerability of VNS therapy in patients with gastroparesis and functional dyspepsia.

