#### ***II. Secondary Study Endpoints***

- 2.1 The effect of VNS therapy on overall pain interference as assessed by the PROMIS pain interference questionnaire
- 2.2 The effect of VNS therapy on overall wellbeing and health as assessed by the short form 12 (SF-12).
- 2.3. The safety and tolerability of VNS in patients with gastroparesis will be assessed by recording any side effects or adverse events.
- 2.4 The effect of VNS therapy on vagal tone as assessed by heart rate variability (HRV) and respiratory variability using electrocardiogram (ASNAR) device and an HRV App called Heart Rate Variability Camera.
- 2.5 The effect of VNS therapy on systemic inflammation as measured by serum inflammatory markers and cytokines (as assessed by the Human 63-plex assay), as well as by activation markers in circulating leukocytes by flow cytometry.

2.6 The effect of VNS therapy on gastric and small intestine inflammation as measured by endoscopy biopsy tissue expression of inflammatory mediators (cytokines, chemokines, etc), and tissue infiltration of immune cells by flow cytometry and immunohistochemistry.

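### The baseline biopsy may be taken up to 8 weeks before VNS starts but baseline emptying is measured on Day 0, so the tissue change can span up to 84 days against about 31 for emptying

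*Combined protocol and SAP*

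**What the plan says.** The schedule table under Study Assessment and Monitoring heads the first endoscopy column "≤ 8 wk prior (baseline) Visit 2 Endoscopy". Section 3.4 gives a pre-treatment period of the same length: "Up to 8 weeks for screening period and baseline measures". Section 4.5 fixes the order of events but not the spacing: "After baseline endoscopy is completed, patients will return to clinic for blood sample collection". That clinic visit is "Day 0 (start VNS) Visit 3 Clinic", where the table places baseline blood, HRV and gastric emptying.

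After treatment the timing is tight. Section 5.2, item 6 states "Patients will present to endoscopy for their post-treatment upper endoscopy 4 weeks after initiation of therapy", and then "No later than 3 days after endoscopy, patients will present to clinic at which time post-treatment gastric emptying testing".

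The two biopsies feed secondary endpoint 2.6, "The effect of VNS therapy on gastric and small intestine inflammation as measured by endoscopy biopsy tissue expression of inflammatory mediators", and also Objective 5 and exploratory endpoint 3.3. Objective 7 joins the tissue and functional data: "Determine if gastric emptying and symptom response to VNS is associated with changes in inflammatory markers and neuro-immune signaling". The statistical analysis plan (Section 7) covers GCSI, gastric emptying and subgroup differences. It has no analysis for Objective 7 and no rule for a variable gap between the first biopsy and Day 0.

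**The concern.** A pre-post change can be read as a treatment effect only to the extent that the interval between the two measurements is the treatment interval. Here the second biopsy is tied to Day 28 but the first can fall anywhere in a window of up to 8 weeks. Emptying is measured on the day treatment starts and again by about Day 31. After treatment the protocol pairs tissue and emptying within 3 days; at baseline it leaves the same pairing open by up to 56 days.

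Two things are at stake. First, the study has no control group, so any tissue change between the first biopsy and Day 0 is added to the apparent VNS effect in endpoint 2.6. Second, for the tissue part of Objective 7, that pre-treatment change enters the tissue difference but not the emptying difference, and by an amount that varies between patients. The gap could also differ by subgroup: diabetic patients with high blood sugar must reschedule the emptying test, which follows the endoscopy and precedes the first stimulation.

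**Working it through.** **Inputs.** Gap g from first biopsy to Day 0: at most 56 days (schedule table; Section 3.4), with no tighter limit stated. Second biopsy: Day 28 (Section 5.2, item 6). Emptying: Day 0, then at most 3 days after the second endoscopy, so up to Day 31 (schedule table; Section 5.2, item 6).

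**Formulas.** Tissue interval = g + 28. Untreated share = g/(g + 28). Ratio to the emptying interval = (g + 28)/31.

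| Gap g (days) | Tissue interval (days) | Untreated share | Ratio to 31 days | Random-walk factor |
|---|---|---|---|---|
| 0 | 28 | 0% | 0.90 | 1.00 |
| 3 | 31 | 9.7% | 1.00 | 0.95 |
| 7 | 35 | 20% | 1.13 | 0.89 |
| 14 | 42 | 33% | 1.35 | 0.82 |
| 28 | 56 | 50% | 1.81 | 0.71 |
| 42 | 70 | 60% | 2.26 | 0.63 |
| 56 | 84 | 67% | 2.71 | 0.58 |

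The untreated part is the larger part only when the gap exceeds 28 days.

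**Effect on an association (illustration, by assumption).** The documents give no variance or drift for any tissue marker. Suppose a marker moves as a random walk with the same variance per day throughout, that its movement before Day 0 is unrelated to response, and that every patient has gap g. The tissue change then has variance proportional to g + 28, while only the 28 treated days share anything with response. A true correlation is multiplied by sqrt(28/(g + 28)), the last column. At g = 56 this is sqrt(28/84) = 0.58.

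Take a true correlation of 0.50 in all 45 patients, two-sided 5% level, using the Fisher transformation:
- No shrinkage: atanh(0.50) × sqrt(42) − 1.96 = 1.60, so power is about 94%.
- g = 56: 0.50 × 0.577 = 0.29; atanh(0.289) × sqrt(42) − 1.96 = −0.03, so power is about 49%.
- g = 14: 0.50 × 0.816 = 0.41; atanh(0.408) × sqrt(42) − 1.96 = 0.85, so power is about 80%.

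If the markers do not drift, the factor is 1.0 at every gap. The range is therefore 0.58 to 1.0 under these assumptions. Patients with mixed gaps would fall between the rows.

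The plan states no figure for this point, so there is none to reproduce.

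**The case against.** The strongest reply has five parts.

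- **The 8 weeks may cover all of screening.** Section 3.4 gives it for the whole screening and baseline period, and the table header is visibly broken in the extracted text. If the limit runs from Visit 1, the biopsy gap is shorter by the wait from consent to endoscopy. This stands: 84 days and 67% are outer bounds. A reader might infer that most of the tissue interval is usually untreated. That needs gaps above 28 days, and the documents give no actual gaps.
- **Symptoms and serum.** A reader might extend the mismatch to all of Objective 7. The documents do not support that. Baseline serum is drawn on Day 0, so the serum part is aligned at baseline. The symptom forms are scheduled at Visits 1 and 3, on either side of the biopsy, and the GCSI diary baseline is placed at enrolment, 1 week before or 2 weeks before in different places. A symptom mismatch is therefore not clearly shown.
- **Drift is assumed.** A reader might take the exclusion of severe flares, or the as-needed medication allowed in Section 5.5, as evidence that tissue markers fluctuate. Neither says anything about biopsy markers. Doses must be stable for 4 weeks before enrolment (Section 4.3) and during the study (Section 5.5), which limits one source of drift. A loss of association is possible, not established.
- **A shorter gap does not supply a control.** True. Change during the 28 treated days remains confounded with VNS, and a 14-day gap still leaves up to 14/42 = 33% untreated. The fix reduces the problem but does not cure it.
- **This is a pilot and the tissue endpoints are secondary or exploratory.** Also true, and both primary endpoints are untouched.

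What survives is the mismatch between tissue and emptying, and the untreated time counted in endpoint 2.6. No section sets a tighter limit or an adjustment.

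**Conclusion.** The point holds for endpoint 2.6 and for the tissue-versus-emptying part of Objective 7. The tissue interval can run from about 28 to 84 days, up to 67% of it untreated and up to 2.7 times the emptying interval. These figures are date arithmetic and rest only on reading the 8 weeks as the limit for the endoscopy; if it runs from Visit 1, the maximum is somewhat lower.

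The statistical consequence is conditional. Any tissue change before Day 0 is attributed to VNS, but its size is unknown. The shrinkage of a correlation, to between 0.58 and 1.0 of its true value, depends on the random-walk assumption at one end and on no drift at the other. The plan should be changed because the remedy is cheap, not because bias has been shown. It would be wrong to conclude that the tissue results are invalid, or that the GCSI and emptying comparisons are affected.

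**What to change.** Keep the 8-week screening period. Change the Visit 2 column so that the baseline endoscopy is booked within 14 days before Day 0, with a target of 7 days, by booking the two visits together. Fourteen days is a judgement rather than a derived figure; it matches the 2-week diary baseline in the schedule, so the biopsy would fall inside the diary period. It cuts the maximum tissue interval from 84 to 42 days and the maximum untreated share from 67% to 33% (20% at 7 days).

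State what happens if Day 0 slips, for example because an emptying test is rescheduled: no repeat endoscopy, and the patient stays in the tissue analysis.

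Add to Section 7 that the biopsy-to-Day-0 interval is recorded and reported by subgroup. Endpoint 2.6 and the tissue part of Objective 7 are then repeated as a sensitivity analysis, either with the interval as a covariate or without gaps over 14 days. For patients already enrolled, this needs only the visit dates.

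Cost: a table edit, a short addition to the analysis plan, less scheduling flexibility, and a smaller sample in the sensitivity analysis if long gaps are excluded, which matters with 15 patients per subgroup. Using the interval as a covariate keeps everyone in. No procedure is added.
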